### 7.2.5 Sponsor Responsibility for Reporting Adverse Events

All Adverse Events will be reported to regulatory authorities, IRB/IECs and investigators in accordance with all applicable global laws and regulations, i.e., per ICH Topic E6 (R1) Guidelines for Good Clinical Practice.

Click here to enter text.

## 8.0 STATISTICAL ANALYSIS PLAN

### 8.1 Statistical Analysis Plan Summary

This section contains a brief summary of the statistical analyses for this trial. Full details are provided in the remainder of Section 8.

Study Design Overview	Phase 1 Trial of Single Agent MK-1248 and MK-1248 in combination with Pembrolizumab in Subjects With Advanced Solid Tumors
Analysis Populations	Safety: All Subjects as Treated (ASaT) Efficacy (exploratory): Single Agent MK-1248 Full Analysis Set (FAS1), MK-1248 in combination with Pembrolizumab Full Analysis Set (FAS2)
Primary Endpoint(s)	Safety: DLT
Key Secondary Endpoints	PK parameters of single agent MK-1248 and MK-1248 in combination with pembrolizumab and PK parameters of pembrolizumab for subjects treated with MK-1248 in combination with pembrolizumab; target engagement as measured by modulation in peripheral blood GITR receptor availability alone and in combination with pembrolizumab
Statistical Methods for Key Efficacy/Immunogenicity/ Pharmacokinetic Analyses	Serum concentrations of MK-1248 in the MK-1248 monotherapy arm and serum concentrations of MK-1248 and pembrolizumab in the MK-1248 and pembrolizumab combination arm will be summarized by planned visit and time for each dose separately; PK parameters will be summarized by dose
Treatment Assignment	Subjects are allocated to increasing doses of single agent MK-1248 and MK-1248 co-administered with pembrolizumab without randomization centrally through IVRS; the study is open-label
Statistical Methods for Key Safety Analyses	Summary statistics (counts, percentage, mean, standard deviation, etc.) will be provided for the safety endpoints as appropriate. The estimate of the DLT rate among subjects treated with the recommended MK-1248 Phase 2 dose and the 95% Bayesian Probability Interval (PI) for the estimate will be provided.
Interim Analyses	Study has no interim analyses
Multiplicity	No multiplicity adjustment is planned in this Phase 1/1b study.
Sample Size and Power	The sample size of the dose acceleration, dose escalation, and dose confirmation (Parts A-E) depends on the observed DLT profiles of MK-1248 monotherapy and MK-1248 co-administered with pembrolizumab. The sample size of 96 subjects that will be obtained if no DLTs are observed will be used for study planning purposes. In certain low probability scenarios, more than 96 subjects will be needed.

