## 1.0 TRIAL SUMMARY

Abbreviated Title	Phase 1 Trial of MK-1248 as Monotherapy and in Combination with Pembrolizumab in Subjects with Advanced Solid Tumors
Trial Phase	Phase 1
Clinical Indication	Treatment of subjects with advanced solid tumors
Trial Type	Interventional
Type of control	None
Route of administration	Intravenous
Trial Blinding	Unblinded Open-label
Treatment Groups	Subjects will be allocated by non-random assignment to one of 2 treatment arms: Arm 1: MK-1248 as monotherapy Arm 2: MK-1248 in combination with pembrolizumab
Number of trial subjects	Approximately 96 subjects will be enrolled.
Estimated duration of trial	The sponsor estimates that the trial will require approximately 4 years from the time the first subject signs the informed consent until the last subject's last visit.
Duration of Participation	Each subject will participate in the trial from the time the subject signs the Informed Consent Form (ICF) through the final contact. After a screening phase of up to 28 days, each subject will be allocated by non-random assignment into one of two arms and receive treatment with MK-1248 alone or in combination with pembrolizumab. Study treatment in both arms will begin on Day 1 of each 3-week cycle. For subjects enrolled in Arm 1 and Arm 2, treatment with MK-1248 will end after 4 cycles; treatment with pembrolizumab in Arm 2 will continue for up to 24 months. Treatment in both arms will continue until disease progression, unacceptable adverse event(s), intercurrent illness that prevents further administration of treatment, Investigators decision to withdraw treatment, subject withdraws consent, pregnancy of the subject, noncompliance with study treatment or procedure requirements, subject completes treatment, or administrative reasons requiring cessation of treatment. After the end of treatment, each subject will be followed for 30 days for adverse event monitoring (serious adverse events will be collected for 90 days after the end of treatment, or 30 days after the end of treatment if the subject initiates new anticancer therapy, whichever is earlier).

Enrollment into this study has been prematurely discontinued due to program prioritization and not related to any safety concerns. The cut-off date for enrollment is 31-Mar-2017.

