MK-4166 is a humanized IgG1 agonist monoclonal antibody being evaluated in an ongoing Phase 1 trial in adults with advanced solid tumors. As of 01-Mar-2017, human safety data are available for a total of 81 patients: 45 patients treated with MK-4166 monotherapy and 36 patients treated with MK-4166 in combination with pembrolizumab. Dose escalation has reached 670 mg in the monotherapy treatment arm and 480 mg in the combination treatment arm. Treatment has generally been well tolerated. One DLT was reported in the MK-4166 monotherapy arm at the 30 mg dose: a patient with metastatic urethral cancer had a Grade 3 perforation of an Indiana Pouch which was considered possibly related to study drug, as the

rate of spontaneous perforation is extremely low and there is no other obvious explanation for the event. Dose escalation is continuing per protocol.

MK-1248 has a similar GITR binding region to MK-4166, while the framework for MK-1248 is an IgG4 class compared to the IgG1 class for MK-4166. As such, MK-4166 has ADCC and CDC activity related to the IgG1 backbone while MK-1248 does not. It is unknown whether the activity of the IgG1 in MK-4166 will result in increased efficacy, increased toxicity, or both. If the IgG1 class molecule results in greater toxicity related to the backbone, then an IgG4 class molecule such as MK-1248 may have a greater therapeutic index. By studying both MK-4166 and MK-1248 in clinical trials, the potential difference in therapeutic index based on the IgG subtype will be assessed and a determination made whether one subtype should be favored for further development.

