## 5.2 Trial Treatment(s)

The treatment(s) to be used in this trial are outlined below in [Table 2](#) and [Table 3](#).

In Arm 1, Part A, dose escalation will begin with 0.12 mg in cohorts of 2 subjects each, and will proceed based on safety events to a dose of 10 mg. Starting at a 30 mg dose (or at a lower dose as described in Section 5.2.1.3) in Part B, dose escalation will continue with a 3+3 design to identify a preliminary maximum tolerated dose (MTD). In Part C, dose confirmation will refine the estimate of the tolerability of the MTD (or maximum administered dose), using a toxicity probability interval [1].

Enrollment to Arm 2, (MK-1248 in combination with pembrolizumab) will begin once 2 subjects complete 1 cycle of MK-1248 monotherapy at the  $\geq 3$  mg dose level in Part A, and will follow a 3+3 design to identify a preliminary MTD in Part D. The starting dose of MK-1248 will be 0.12 mg. Doses of MK-1248 will be escalated as described in [Table 3](#) and the dose of pembrolizumab will be fixed at 200 mg. During 3+3 dose escalation, at least 2 days of observation will occur between each of the first 3 subjects at each dose level (except for the first 2 subjects receiving the combination treatment at the first dose level for which at least 7 days of observation between dosing will occur). Dose confirmation in Part E will refine the estimate of tolerability of the MTD using a toxicity probability interval [1].

Enrollment to both arms will occur in parallel with treatment allocation accomplished by non-random assignment to Arm 1 or Arm 2 using an IVRS/IWRS.

If pharmacodynamic saturation at the tissue level and/or robust clinical efficacy is observed during the dose escalation phase in either the monotherapy or combination therapy arm, initiation of the dose confirmation Parts C and E may begin. Depending on safety, efficacy and pharmacologic data, dose escalation in the monotherapy and combination therapy arms may continue concurrent with enrollment in Parts C and E. Up to a total of 14 subjects may be enrolled at a lower dose level where robust clinical activity is observed concurrent with the dose escalation phase. In either of the above cases, an administrative letter will be used to document the initiation of a dose confirmation cohort (Part C or E for the monotherapy or combination treatment, respectively), or to allow enrollment of up to a total of 14 subjects at a given dose.

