### 5.2.4 Replacement of Subjects During DLT Evaluation Period

In order to determine safety, all subjects selected must meet the criteria for evaluability for Cycle 1. Subjects are considered non-evaluable for DLT assessment and will be replaced if:

- They are enrolled but not treated
- They discontinue from the trial prior to completing all the safety evaluations for reasons other than treatment-related adverse events
- They receive less than 90% of the total MK-1248 or pembrolizumab infusion in Cycle 1 ( e.g., because the infusion had to be discontinued due to an infusion reaction) and did not experience a DLT

Non-evaluable subjects will not be counted toward the cohort total for DLT evaluation.

If a subject experiences a DLT in Cycle 1, study treatment may be discontinued following discussion between the sponsor and Investigator. However, if the subject is deriving clinical

benefit from the study treatment, the subject may be allowed to continue after discussion between the sponsor and the Investigator.

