### **8.9 Sample Size and Power Calculations**

#### **8.9.1 Dose Escalation and Dose Confirmation**

The primary purpose of the dose escalation and dose confirmation parts of the trial is to investigate the safety and tolerability of MK-1248 monotherapy and MK-1248 co-administered with pembrolizumab in adult subjects with advanced solid tumors (Parts A-E) and to establish RP2Ds for MK-1248 monotherapy and MK-1248 co-administered with pembrolizumab.

The final number of subjects enrolled in the dose escalation and confirmation parts of the study will depend on the empirical safety (DLT) observations, in particular, at what dose the 3+3 design is triggered and what dose is identified as the RP2D. Sample sizes for a few possible scenarios as well as the estimated time required to enroll all subjects and the time

required to determine the MTD are provided below. The time required to estimate the MTD is the time from the first subject's first dose to the end of the 3-week observation period following the first dose of the last subject enrolled in the dose confirmation part. The study duration is derived as the time from the first subject's first dose to the end of 2-year treatment period following the enrollment of the last Part E subject.

The enrollment time was conservatively estimated assuming that during dose acceleration part it will take 4 weeks to proceed from one dose to the next and during 3+3 parts and that during the dose confirmation a subject can be enrolled every week.

Scenario 1. No DLTs during Parts A-E. For MK-1248 monotherapy, in a scenario where no DLTs are encountered during the dose escalation and confirmation parts and thus Part B continues to the highest dose in [Table 2](#), the sample size across Parts A-C is 46 subjects (8 subjects in Part A, 27 subjects across 9 doses in Part B, and 11 subjects on RP2D in Part C). For MK-1248 with pembrolizumab, in a scenario where Arm 2 starts at 0.12mg MK-1248 and 200 mg pembrolizumab and no DLTs are encountered during the dose escalation and confirmation parts so that Part D continues to the highest dose in [Table 2](#), the sample size across Parts D and E is 50 subjects (39 subjects across 13 doses in Part D, and 11 subjects on RP2D in Part E). The total sample size across Parts A-E is 96 subjects.

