Scenario 3. Early start of 40% dose increments for Arm 2. If in Arm 2, 40% increments in the 3+3 design doses are triggered at 3 mg dose and dose escalation continues in 18 steps to 915 mg dose, with 3 subjects per dose in 3+3 design and 11 subjects in Part C, the sample size of Arm 2 across Parts D and E is 65 (54 in Part D and 11 in Part E). Suppose that dose escalation in Arm 1 proceeds without DLTs as in Scenario 1, and thus, the sample size of Arm 1 across Parts A-C is 46 subjects (8 subjects in Part A, 27 subjects across 9 doses in Part B, and 11 subjects on RP2D in Part C). The total sample size across Parts A-E is 111 subjects.

It will take 16 weeks to enroll 8 MK-1248 monotherapy subjects in Part A and proceed to Part B enrolment; it will take additional 103 weeks to enroll 103 subjects (38 in Parts B and C and 65 in Parts D and E). Thus, in this scenario the enrollment time across Parts A-E is 135 weeks and the time required to determine the two MTDs is 122 weeks. The study duration then is approximately 125 weeks + 2 years or 4.3 years.

The plausible sample size of approximately 96 subjects and the enrollment time of 104 weeks (study duration of 4 years) that correspond to the first described scenario are used for operational purposes.

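### Section 8.1 calls exceeding 96 subjects a low-probability event, but 96 is the no-DLT, no-replacement count, and with full escalation it is exceeded about half the time or more at DLT rates of roughly 1% to 5%

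*Combined protocol and SAP*

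**What the plan says.** - Section 1.0: "Approximately 96 subjects will be enrolled".
- Section 8.1 gives the basis of that figure: "The sample size of 96 subjects that will be obtained if no DLTs are observed will be used for study planning purposes". It then adds: "In certain low probability scenarios, more than 96 subjects will be needed".
- Section 8.9.1, Scenario 1, builds Arm 1 as "8 subjects in Part A, 27 subjects across 9 doses in Part B, and 11 subjects on RP2D in Part C", which is 46. Arm 2 is 39 in Part D plus 11 in Part E, which is 50. Two larger scenarios have stated totals of 118 and 111, and one smaller example (both arms stopping at 330 mg) has 78. None carries a probability or a DLT rate. The section closes by adopting "The plausible sample size of approximately 96 subjects and the enrollment time of 104 weeks".
- Section 5.2.4: "Subjects are considered non-evaluable for DLT assessment and will be replaced if" one of three listed conditions applies. Such subjects do not count toward the cohort total.
- Section 5.2 also allows an optional expansion: "Up to a total of 14 subjects may be enrolled at a lower dose level where robust clinical activity is observed".
- Section 4.1.1.1, on the related antibody: "One DLT was reported in the MK-4166 monotherapy arm at the 30 mg dose". Data were available for 81 patients, 45 of them on monotherapy.

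**The concern.** A total that assumes no DLT and no replacement has no slack. In a 3+3 design the ordinary consequence of one stray DLT is three more subjects at that dose, after which escalation continues. Exceeding 96 therefore looks like a common result rather than a tail event, unless DLTs are very rare, are frequent enough to stop escalation early, or escalation ends early for another reason.

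What is at stake is the accuracy of a stated property of the design. A reader of Section 8.1 would take 96 as close to an upper planning figure, when under full escalation it is nearer the middle of the distribution at low DLT rates. No dose decision, RP2D rule or precision statement depends on the sentence.

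**Working it through.** **1. Reproduce 96.** Arm 1: 4 × 2 + 9 × 3 + 11 = 46. Arm 2: 13 × 3 + 11 = 50. Total 96, as stated.

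**2. Add one DLT.** Under Section 5.2.1.4, 1/3 with a DLT brings three more subjects, and 1/6 escalates. Suppose this happens once, at 60 mg in Arm 1. Part B becomes 8 × 3 + 6 = 30, Arm 1 becomes 8 + 30 + 11 = 49, and the total is 49 + 50 = 99. At the top dose the same event adds nothing, because that dose is filled to 14 in any case (6 + 8 instead of 3 + 11). The levels that matter are the 8 lower doses in Part B and the 12 lower doses in Part D, 20 in all. A Part A pair with a DLT can also grow from 2 to 6.

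**3. Hand approximation.** Ignoring Part A and early stopping, P(at least one of the 20 cohorts has exactly 1/3) = 1 − (1 − 3p(1−p)²)^20.
- p = 1%: 1 − (1 − 0.0294)^20 = 0.45.
- p = 1/81: 0.52.

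At higher rates the formula overshoots, because it ignores stopping.

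**4. Simulation of the rules.** The model has Part A pairs, 3+3 with termination at 2 or more DLTs, confirmation to 14 using the Table 4 de-escalation boundaries, and the dose ladder of Tables 2 and 3. It has no re-escalation and no replacements, and only DLTs stop escalation. The documents give no DLT rate for MK-1248, so the rates are assumptions. The values 1/81 and 1/45 are the related antibody's crude proportions. With 8,000 trials per setting the Monte Carlo standard error is at most √(0.25/8000) = 0.006.

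| Flat DLT rate | P(N > 96) | Mean N | P(N > 105) |
|---|---|---|---|
| 0.5% | about 28% | | |
| 1% | about 47% | | |
| 1/81 (1.2%) | about 54% | 97.9 | about 3% |
| 1/45 (2.2%) | about 67% | 98.1 | about 8% |
| 3% | about 70% | 97.5 | about 13% |
| 5% | about 58% | 93.6 | about 22% |
| 10% | about 20% | | |

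The 90th percentile is about 102 to 110 over 1/81 to 5%. The 50% line is crossed near 1.1% and again at about 5.5% or higher.

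**5. Sensitivity.**
- Runs with and without the cap of Arm 2 at the monotherapy MTD, and with different readings of when the 40% increments start, give 0.47 at 1%, 0.65–0.67 at 2%, 0.69–0.73 at 3%, 0.55–0.66 at 5% and 0.17–0.31 at 10%. An early switch to 40% increments can raise the 90th percentile to about 153.
- Rates rising from the lowest to the highest dose give 0.56 (0.5% to 2%), 0.66–0.68 (0.5% to 5%), 0.49–0.58 (1% to 10%) and 0.05–0.19 (1% to 30%).
- If both arms stop at 330 mg, six cohorts of 3 drop out, so the base is 96 − 18 = 78. P(N > 96) is then about 1% or less at rates up to 5%.

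**6. Replacements.** Take no DLTs and an independent non-evaluable rate q. The documents give no rate, so q is assumed. P(N > 96) = 1 − (1 − q)^96.
- q = 1%: 1 − 0.99^96 = 0.62.
- q = 2%: 1 − 0.98^96 = 0.86.
- q = 5%: 1 − 0.95^96 = 0.99.

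Expected enrolment is 96/(1 − q): about 97, 98 and 101.

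**The case against.** The best defence has four parts.

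- **The sentence may point to the large scenarios.** If it refers to the stated totals of 118 and 111, it is fair: without replacements or early 40% increments, P(N ≥ 111) is 10% or less at every flat rate run. But the sentence names 96 as its threshold, not 111.
- **The plan describes stopping for reasons other than DLTs.** Section 8.9.1 works the 330 mg example, and Section 4.2.2.3 puts the predicted efficacious range at 60 to 330 mg. Under that stop, low probability is the right description. This stands, and it makes every percentage in the table conditional on escalation to 900 mg unless DLTs intervene. The planning figure of 96 carries the same condition.
- **The figure is approximate and the overrun small.** This also stands. Mean N stays near 96, and a total more than 10% above it is uncommon at rates up to 3%.
- **The DLT rate is unknown.** One DLT in 81 patients on another molecule has an exact 95% interval of about 0.03% to 6.7%, and Section 4.2.2.1 predicts less Fc-related activity for MK-1248. At 0.5%, or at 10% and above, exceeding 96 is the less likely outcome.

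Three stronger readings are tempting and are not supported. A reader might infer that 96 is exceeded more often than not throughout 1% to 5%; at exactly 1% the figure is 47%. A reader might take near-certainty from the replacement calculation, but that rests on non-evaluable rates the documents do not give. And a reader might suppose that the 104 weeks and 4 years depend on the disputed sentence; Section 8.9.1 takes them from Scenario 1.

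**Conclusion.** The concern holds in a limited form, and it is minor. The figure of 96 is arithmetically right as the no-DLT, no-replacement count under full escalation. Calling an excess over it improbable is not right under the protocol's own rules when escalation runs to 900 mg unless DLTs stop it: the probability is about 47% to 70% for flat DLT rates of 1% to 5%, before any replacement. The description is fair at DLT rates of about 10% or more, with steep dose-toxicity, or with a stop at 330 mg. Separately, replacements required by Section 5.2.4 appear in no scenario, and even a 1% non-evaluable rate (assumed) makes exceeding 96 more likely than not with no DLT at all.

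The expected size is close to what was planned; it is the probability statement that is wrong. Enrolment closed on 31-Mar-2017, so nothing here bears on the conduct of the trial.

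**What to change.** - **Section 8.1:** delete the words *low probability*. State that 96 is the count for full escalation in both arms with no DLT and no replaced subject.
- **Section 8.9.1:** add a short table of the mean and 90th percentile of enrolled subjects over stated DLT rates (for example 0.5% to 10%), with and without the 330 mg stop, and over assumed non-evaluable rates labelled as such. Note that the optional lower-dose expansion in Section 5.2 is additional. While editing, reconcile the Scenario 2 total: the stated arms are 58 and 68, which sum to 126, not 118; the difference is the 8 Part A subjects.
- **Leave alone:** the 104-week and 4-year figures, as Scenario 1 values. A new accrual forecast would serve no purpose after enrolment has closed.

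The cost is a few sentences and a small simulation. No design rule, analysis or decision boundary changes.

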## 8.2 Responsibility for Analyses/In-House Blinding

The statistical analysis of the data obtained from this study will be the responsibility of the Clinical Biostatistics department of the SPONSOR.

This trial is conducted as an open-label trial, i.e., subjects, investigators, and SPONSOR personnel will be aware of subject treatment assignments after each subject is enrolled and treatment is assigned. Allocation to treatment will not be randomized.

The database will be locked for analysis when all subjects who have not discontinued due to progression, death or withdrawal of consent are at least 6 months after their first dose.

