#### 3.1 Primary Objective(s)

- 1) **Objective:** To determine the safety and tolerability of MK-1248 monotherapy and to establish a maximum tolerated dose (MTD) or maximum administered dose (MAD)
- 2) **Objective:** To determine the safety and tolerability of MK-1248 monotherapy and to establish a maximum tolerated dose (MTD) or maximum administered dose (MAD) when given in combination with pembrolizumab

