12. In Arm 1 and Arm 2, on Day 1 in cycles 1-4, CBC with differential, CRP and chemistry profile should be drawn prior to dosing and repeated 4 hours after the start of the MK-1248 infusion, with results of the CBC and chemistry profile reviewed by the PI or appropriate designee before the subject is discharged from the clinic. In Arm 2, beginning with Cycle 5, CBC with differential, CRP and chemistry profile should be drawn prior to dosing.
13. For women of reproductive potential, a urine pregnancy test will be performed at Screening and within 24 hours prior to the first dose of study treatment. If a urine pregnancy test cannot be confirmed as negative, a serum pregnancy test is required.
14. Thyroid function testing is to be performed starting in Cycle 1 and then every other cycle and at the Post treatment safety follow-up visit
15. Include HCV, RNA (qualitative) or Hepatitis C antibody, HBsAg, and HIV type 1 and type 2 (e.g., HIV-1/2 antibody screening test and evaluation of HIV viral load as needed).
16. Collect humoral immunity assays prior to dosing in Cycles 1-4 in Arm 1 and Cycles 1-6 in Arm 2 (specific assays designated in procedures manual).
17. For Arm 1, collect cytokine panels for cycles 1-4 on day 1 predose, 1 hour and 4 hours post infusion, and on day 2 and day 3. For Arm 2, collect cytokine panels for cycles 1-4 on day 1 predose, 1 hour and 4 hours post infusion, and on day 2 and day 3. For Cycles 5 and 6, collect samples on day 1 Predose, 1hour and 4 hour post infusion.
18. MK-1248 Anti-drug antibody (ADA) will be drawn in Arm 1, predose MK-1248 on Day 1, Day 2, Day 3, Day 8 and Day 15 of Cycles 1-4, and at the Safety visit 30 days post discontinuation and at 3 months and 6 months after the last dose . In Arm 2 MK-1248 ADA will be obtained predose MK-1248 on Day 1, on Day 2, Day 3, Day 8 and Day 15 of Cycles 1-4, predose pembrolizumab Cycles 5, and 6, and at the Safety visit 30 days post discontinuation and at 3 months and 6 months after the last dose .

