##### **7.1.8.2 Treatment Period**

Visit requirements are outlined in Section 6.0 - Trial Flow Chart. Specific procedure-related details are provided above in Section 7.1 - Trial Procedures.

After a screening phase of up to 28 days, eligible subject will be assigned to one of 2 Arms and a dose level of MK-1248 by IVRS. In Arms 1 and 2, MK-1248 treatment will be administered on Day 1 of each 21-day cycle for up to a maximum of 4 cycles. In Arm 2, pembrolizumab will be administered on Day 1 of each 21 day cycle for up to 24 months of treatment.

Subjects will be followed until confirmed disease progression, unacceptable adverse event(s), intercurrent illness that prevents further administration of treatment, investigator's decision

to withdraw the subject, subject withdraws consent, pregnancy of the subject, noncompliance with study treatment or procedure requirements, or administrative reasons.

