### 7.2.3 Immediate Reporting of Adverse Events to the Sponsor

#### 7.2.3.1 Serious Adverse Events

A serious adverse event is any adverse event occurring at any dose or during any use of Sponsor's product that:

- Results in death;
- Is life threatening;
- Results in persistent or significant disability/incapacity;
- Results in or prolongs an existing inpatient hospitalization;
- Is a congenital anomaly/birth defect;
- Is an other important medical event.

**Note:** In addition to the above criteria, adverse events meeting either of the below criteria, although not serious per ICH definition, are reportable to the Sponsor in the same timeframe as SAEs to meet certain local requirements. Therefore, these events are considered serious by the Sponsor for collection purposes.

- Is a new cancer (that is not a condition of the study);
- Is associated with an overdose.

Refer to [Table 9](#) for additional details regarding each of the above criteria.

Progression of the cancer under study is not considered an adverse event unless it results in hospitalization or death.

For the time period beginning when the consent form is signed until randomization/treatment allocation, any serious adverse event, or follow up to a serious adverse event, including death due to any cause, that occurs to any subject must be reported within 24 hours to the Sponsor if it causes the subject to be excluded from the trial, or is the result of a protocol-specified intervention, including but not limited to washout or discontinuation of usual therapy, diet, placebo treatment or a procedure.

For the time period beginning at randomization/treatment allocation through 90 days following cessation of treatment, or 30 days following cessation of treatment if the subject initiates new anticancer therapy, whichever is earlier, any serious adverse event, or follow up to a serious adverse event, including death due to any cause, whether or not related to the Sponsor's product, must be reported within 24 hours to the Sponsor either by electronic media or paper. Electronic reporting procedures can be found in the EDC data entry guidelines. Paper reporting procedures can be found in the Investigator Trial File Binder (or equivalent).

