### **8.7 Interim Analyses**

No interim analyses are planned for this study.

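### The only database lock is timed from first dose and can precede planned late safety and PK/ADA data, mainly in late-enrolled subjects and those still on pembrolizumab

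*Combined protocol and SAP*

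**What the plan says.** Section 8.2 (Responsibility for Analyses/In-House Blinding) gives one lock rule. The database is locked "when all subjects who have not discontinued due to progression, death or withdrawal of consent are at least 6 months after their first dose". Section 8.7 adds: "No interim analyses are planned for this study". No section describes a second lock, a final lock or an update of the outputs.

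The data to be analysed follow a different clock:

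- MK-1248: "MK-1248 treatment will be administered on Day 1 of each 21-day cycle for up to a maximum of 4 cycles" (Section 7.1.8.2).
- Pembrolizumab in Arm 2: "pembrolizumab will be administered on Day 1 of each 21 day cycle for up to 24 months of treatment" (Section 7.1.8.2; Section 1.0 agrees). Section 4.2.2.4.2 gives 24 weeks instead.
- PK and ADA samples: "at the Safety visit 30 days post discontinuation and at 3 months and 6 months after the last dose" (Section 6.0, footnote 18 for MK-1248 ADA; footnotes 19 to 21 use the same time points).
- All adverse events: to 30 days after treatment ends (Section 7.2).
- Serious adverse events: "For the time period beginning at randomization/treatment allocation through 90 days following cessation of treatment", or 30 days if new anticancer therapy starts first (Section 7.2.3.1). Section 7.2.3.2 sets the same window for events of clinical interest (ECIs).

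Section 8.9.1 counts the trial's duration to "the end of 2-year treatment period following the enrollment of the last Part E subject".

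**The concern.** The lock runs from first dose, and the follow-up it has to capture runs from last dose. A subject enrolled near the end can satisfy the lock rule with planned visits still to come. A subject who has left for progression does not hold up the lock at all.

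Both primary objectives begin "To determine the safety and tolerability of MK-1248 monotherapy", the second of them for use with pembrolizumab. Sections 5.2.3.1 and 5.2.3.2 warn that immune-related events may appear several months after the last dose, so late safety data are part of what the trial is for. PK is a key secondary endpoint, summarised by planned visit and time (Sections 8.1 and 8.6.3.2). Extent of exposure is the total number of doses received (Section 8.12), which is not final for anyone still on pembrolizumab. PFS and duration of response, both exploratory, are cut at the same point.

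**Working it through.** **Conventions.** First dose is day 0. One month is 30.44 days, so 6 months is about 183 days (26.1 weeks) and 24 months is 104.4 weeks; 90 days is 12.9 weeks.

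**1. The plan's own timeline (Section 8.9.1, Scenario 1).** Subjects: (8 + 27 + 11) + (39 + 11) = 46 + 50 = 96. Enrolment: 16 + 88 = 104 weeks. Duration: 104 weeks + 2 years = 4.0 years. All three reproduce.

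**2. Earliest lock on that timeline, if the last-enrolled subject still counts.** 104 + 26.1 = week 130, or 2.5 years. The 2-year treatment period of the last subject ends at 104 + 104.4 = week 208, about 78 weeks later.

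**3. The last-enrolled subject, in weeks after first dose (lock at week 26.1).**

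| Case | Last dose | 90-day window closes | 6-month sample |
|---|---|---|---|
| Four MK-1248 doses on time, no pembrolizumab | 9 | 9 + 12.9 = 21.9 (4.2 before lock) | 9 + 26.1 = 35.1 (9.0 after lock) |
| Arm 2, pembrolizumab for 24 weeks in all (Section 4.2.2.4.2) | 21 to 24 | about 34 to 37 | about 47 to 50 |
| Arm 2, pembrolizumab for 24 months (Sections 1.0, 7.1.8.2) | 104.4 | about 117 | about 130 |

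In days, the first row is: last dose 63, window closes 63 + 90 = 153, sample 63 + 183 = 246, lock 183. For a last-enrolled subject, any last dose after week 26.1 − 12.9 = 13.2 leaves the 90-day window open at lock.

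**4. How many subjects.** With four on-time doses, the sample falls after lock for anyone first dosed in the last 246 − 183 = 63 days. At the plan's one subject per week that is 63 / 7 = 9 subjects, if they are still followed.

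**5. A delayed Arm 1 subject.** Table 5 counts its 12-week limit from the last dose. With dose 3 on day 42, a near-maximal hold puts dose 4 at about 42 + 84 = day 126. The window then closes at 126 + 90 = day 216, after day 183.

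**6. Pembrolizumab exposure outstanding across Arm 2 (24-month text).** Assume uniform entry up to week 104 and no discontinuation. Exposure accrued by lock is min(130.1 − entry week, 104.4). Subjects entering before week 25.7 reach the maximum. Later entrants average (104.4 + 26.1) / 2 = 65.2 weeks over a 78.3-week span.

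- Entry from week 16: (9.7 × 104.4 + 78.3 × 65.2) / 88 = 69.6 weeks, or 67% of 104.4.
- Entry from week 12: (13.7 × 104.4 + 78.3 × 65.2) / 92 = 71.1 weeks, or 68%.
- All Arm 2 entries in the last 50 weeks: (76.1 + 26.1) / 2 = 51.1 weeks, or 49%.

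So 32 to 33% of the maximum is outstanding under uniform entry. With exponential discontinuation (assumed median 3 to 24 months), 72 to 95% of expected exposure is accrued at lock under uniform entry and 57 to 92% under late entry. For a last-enrolled subject still on treatment, 26.1 / 104.4 = 25% of the permitted period has passed.

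**7. Subjects off for progression.** Suppose the last-enrolled subject progressed with a last dose at week 9, so the window closes at week 21.9. The lock cuts it only if about the last 5 enrolled subjects have all left for exempt reasons: 26.1 − 5 = 21.1 weeks, which is before 21.9. The other route is an Arm 2 subject who stops for progression within 90 days before lock.

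**The case against.** The best defence is that 8.2 sets a floor and not a date. The sponsor may lock later. Ongoing subjects continue to be followed per protocol (Sections 1.0 and 2.1), and SAE reporting does not stop at a lock. Survival status may be requested throughout (Section 7.1.8.4), publication is timed from when the last data become available (Section 10.7), and data-management detail sits in a separate document (Section 10.6). A reader might infer from 8.2 that late data will be thrown away. The documents do not say that, and silence is not a plan to discard. What remains is that none of these sections supplies a later analysis.

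The sample gap is also softer than the dates suggest. Sections 7.1.4.1 and 7.1.4.2 let the sponsor store PK and ADA samples, analyse them only if required, and reduce or stop collection. Section 5.8 lists confirmed progression among the reasons for leaving the trial (and also among the reasons for stopping treatment only), so some subjects would have no 6-month visit to lose. Both points stand, but neither bears on the adverse-event windows or exposure of subjects still on pembrolizumab.

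Finally, the primary endpoint is DLT within 21 days. For subjects past that period, DLT data are complete long before a 6-month lock. That stands in full.

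**Conclusion.** The point holds for late-enrolled subjects and for Arm 2 subjects on, or recently off, pembrolizumab at lock. Followed at its earliest date, 8.2 leaves out the 6-month PK/ADA sample of about the last 9 subjects. It also leaves out the remaining exposure, adverse events, 90-day SAE/ECI window and PFS and response-duration follow-up of ongoing Arm 2 subjects. The counts rest on Scenario 1 accrual of one subject per week and on-time dosing. Enrolment was in fact closed on 31 March 2017 and actual entry dates are not given. If someone was first dosed at that cut-off, the lock could come about October 2017, with pembrolizumab permitted to about spring 2019.

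Four stronger readings are not supported:

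- That most Arm 2 exposure falls after lock. That describes only the latest entrants. Across the arm it is about one third of the permitted maximum under uniform entry, about half in the extreme late-entry case, and less after discontinuations. If 24 weeks in all is meant, no dosing is lost, though the 90-day window and the 6-month sample still fall after lock. Sections 1.0, 4.2.2.4.2 and 7.1.8.2 must be reconciled.
- That Arm 1 SAE windows are generally cut. On-time windows close at day 153, before lock. Only a long hold carries one past it.
- That the MTD or the DLT estimate at the recommended dose is compromised. Neither depends on data after day 21.
- That the loss falls on the confirmation cohorts. This follows only under Scenario 1 accrual, and the documents do not say whether Parts C or E opened.

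This should be corrected, but it does not undermine the dose-finding result.

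**What to change.** Label the 8.2 lock as the primary-analysis lock. Add to 8.2 a final lock at end of trial as defined in Section 5.10, at which the safety, exposure, PK/ADA, PFS and response-duration outputs are re-run.

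For the primary lock, preferably add a condition covering every treated subject, including those off for progression. The 90-day SAE/ECI window (or its 30-day alternative) and the 6-month PK/ADA point, both counted from the last MK-1248 dose, should have passed. Exceptions are subjects who have died, withdrawn consent or left follow-up, and the PK/ADA part lapses where that sampling has been discontinued. Do not tie the primary lock to the last pembrolizumab dose: each Arm 2 subject who stopped would push it back again, and the final lock covers those data. State which drug's last dose sets the 3- and 6-month samples in Arm 2, since footnote 18 does not say.

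Cost: measured against day 183, the primary lock moves by 246 − 183 = 63 days, about 2 months, with on-time dosing. With a maximal hold it moves by (126 + 183) − 183 = 126 days, about 4 months. One repeat run of existing outputs is needed at trial end. No new data are collected.
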